#### **5.4.1 Supportive Care Guidelines for Pneumonitis**

Subjects with symptomatic pneumonitis should immediately stop receiving pembrolizumab and have an evaluation. The evaluation may include bronchoscopy and pulmonary function tests to

rule out other causes such as infection. If the subject is determined to have study drug associated pneumonitis, the suggested treatment plan is detailed in Table 5.6.

**Table 5.6 Recommended Approach to Handling Pneumonitis**

Study drug associated pneumonitis	Withhold/Discontinue pembrolizumab	Supportive Care
Grade 1 (asymptomatic)	No action	Intervention not indicated
Grade 2	Withhold pembrolizumab, may return to treatment if improves to Grade 1 or resolves within 12 weeks	Systemic corticosteroids are indicated. Taper if necessary.
Grade 3 and Grade 4	Discontinue pembrolizumab	Systemic corticosteroids are indicated. The use of infliximab may be indicated as appropriate. Refer to the Event of Clinical Interest and Immune-related Adverse Event Guidance Document for additional recommendations.

For Grade 2 pneumonitis that improves to  $\leq$  Grade 1 within 12 weeks, the following rules should apply:

- First episode of pneumonitis
  - May increase dosing interval by one week in subsequent cycles
- Second episode of pneumonitis – permanently discontinue pembrolizumab if upon rechallenge subject develops pneumonitis  $\geq$  Grade 2

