#### **Attribution of Toxicity:**

When study interventions are administered in combination, attribution of an adverse event to a single component is likely to be difficult. Therefore, while the investigator may attribute a toxicity event to the combination, to Vorinostat or Tamoxifen alone, or to pembrolizumab alone, for adverse events listed in Table 5.4, both interventions must be held according to the criteria in Table 5.4 Dose Modification and Toxicity Management Guidelines for Immune-Related Adverse Events Associated with Pembrolizumab.

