#### **Restarting Study Interventions:**

Participants may not have any dose modifications (no change in dose or schedule) of pembrolizumab in this study, as described in Table 5.4.

- If the toxicity does not resolve or the criteria for resuming treatment are not met, the participant must be discontinued from all study interventions.
- If the toxicities do resolve and conditions are aligned with what is defined in Table 5.4, the combination of Vorinostat, Tamoxifen and pembrolizumab may be restarted at the discretion of the investigator. In these cases where the toxicity is attributed to the combination or to Vorinostat or Tamoxifen alone, re-initiation of pembrolizumab as a monotherapy may be considered at the PI's discretion.

**Table 5.4 Dose modification and toxicity management guidelines for immune-related AEs associated with pembrolizumab monotherapy and IO Combinations**

irAEs	Toxicity Grade (CTCAE v5.0)	Action With Pembrolizumab	Corticosteroid and/or Other Therapies	Monitoring and Follow-up
Pneumonitis	Grade 2	Withhold	
 
• Administer corticosteroids (initial dose of 1 to 2 mg/kg prednisone or equivalent) followed by taper
 
• Add prophylactic antibiotics for opportunistic infections
 
	
 
• Monitor participants for signs and symptoms of pneumonitis
 
• Evaluate participants with suspected pneumonitis with radiographic imaging and initiate corticosteroid treatment
 

	Recurrent Grade 2, Grade 3 or 4	Permanently discontinue		
Diarrhea/Colitis	Grade 2 or 3	Withhold	
 
• Administer corticosteroids (initial dose of 1 to 2 mg/kg prednisone or equivalent) followed by taper
 
	
 
• Monitor participants for signs and symptoms of enterocolitis (ie, diarrhea, abdominal pain, blood or mucus in stool with or without fever) and of bowel perforation (ie, peritoneal signs and ileus)
 
• Participants with ≥Grade 2 diarrhea suspecting colitis should consider GI consultation and performing endoscopy to rule out colitis
 
• Participants with diarrhea/colitis should be advised to drink liberal quantities of clear fluids. If sufficient oral fluid intake is not feasible, fluid and electrolytes should be
 

	Recurrent Grade 3 or Grade 4	Permanently discontinue		

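### Two sections govern pneumonitis without reference to each other, and they disagree on when steroids start, on the Grade 2 taper and on the pembrolizumab schedule at restart

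*Combined protocol and SAP*

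**What the plan says.** Pneumonitis is handled in two places.

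**Section 5.2.2 and Table 5.4.** The opening text stresses early recognition and treatment of immune-related events. It also asks that suspected events be evaluated to confirm the cause or exclude others, with bronchoscopy among the possible tests. For pneumonitis, Table 5.4 instructs: "Evaluate participants with suspected pneumonitis with radiographic imaging and initiate corticosteroid treatment". Its treatment column reads "Administer corticosteroids (initial dose of 1 to 2 mg/kg prednisone or equivalent) followed by taper" and "Add prophylactic antibiotics for opportunistic infections". The text on attribution says that, for events in the table, "both interventions must be held according to the criteria in Table 5.4", and the next paragraph repeats the hold for immune-related events. The restart text then rules out altering the dose or schedule of pembrolizumab.

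**Section 5.4.1 and Table 5.6.** The section begins: "Subjects with symptomatic pneumonitis should immediately stop receiving pembrolizumab and have an evaluation". The evaluation may include bronchoscopy and lung function tests to rule out causes such as infection. Treatment follows: "If the subject is determined to have study drug associated pneumonitis, the suggested treatment plan is detailed in Table 5.6". At Grade 2 the supportive care is "Systemic corticosteroids are indicated. Taper if necessary". At Grades 3 and 4 it is "Systemic corticosteroids are indicated. The use of infliximab may be indicated as appropriate", with a pointer to an external guidance document for further recommendations. Below the table, after a first Grade 2 episode that improves within 12 weeks, the pembrolizumab interval may be extended by one week in later cycles.

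**The concern.** A protocol can describe one toxicity in two places if the descriptions match or one is said to govern. Here neither holds. Table 5.6 is headed as the recommended approach to this event, so staff could reasonably use it alone, and nothing in Section 5.4.1 sends them back to Table 5.4. Table 5.4 sits in the general section on immune-related events and does not point forward.

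At stake is whether patients with the same event receive the same care. Someone waiting for bronchoscopy could already be on steroids under one section and not yet under the other. A patient restarting after a Grade 2 episode could be put on a longer interval that one section permits and the other forbids, so the same action could be recorded as compliant or as a deviation. Section 5.2.2 itself treats prompt treatment as important, which makes an unclear trigger for steroids worth settling before a case arises.

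**Working it through.** No sample size, power or error rate is involved, so the check is a side-by-side reading.

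| Item | Section 5.2.2 / Table 5.4 | Section 5.4.1 / Table 5.6 | Relation |
|---|---|---|---|
| Steroid start | Imaging and steroids paired, at suspicion | Stop pembrolizumab, evaluate, then treat once judged drug-associated | Differ; sequence unclear |
| Taper, Grade 2 | Always | Only if necessary | Differ |
| Pembrolizumab schedule at restart | No change allowed | Interval may lengthen by one week after a first episode | Differ |
| Starting steroid dose | Range given | Not stated | Instruction against silence |
| Antibiotic prophylaxis | Added | Not stated | Instruction against silence |
| Partner drugs | Both interventions held (section text, not a table cell) | Only pembrolizumab named | Instruction against silence |
| Taper, Grades 3–4 | Always, if the cell spans all grades listed | Not stated; external guidance cited | Silence; cannot be resolved here |
| Withholding and stopping pembrolizumab | Withhold at Grade 2; stop at Grade 3–4 or recurrent Grade 2 | Same in substance | Agree |

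**Steroid start.** The trigger is suspicion in one text and a determination of drug association in the other. The introduction to Section 5.2.2 also wants other causes excluded, so Table 5.4 does not replace evaluation with treatment. What it leaves open is whether steroids begin while evaluation is in progress. Section 5.4.1 points the other way, because steroids first appear in the table that applies after the determination.

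**Taper.** An unconditional taper and a conditional one are different instructions. The Grade 2 comparison does not depend on how the cells of Table 5.4 are merged.

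**Restart.** A permission and a prohibition on the same act cannot both stand. Section 5.1 does allow cycle intervals to be increased for toxicity, but it defers to Section 5.2 for how. The restart text in Section 5.2.2 is the one that bars a schedule change, while the one-week extension sits in Section 5.4.1.

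**Holding vorinostat.** The action column of Table 5.4 names only pembrolizumab, as does that of Table 5.6. The hold on both interventions comes from the text of Section 5.2.2 and is tied to the event, not to the table consulted. Pneumonitis is a listed event, so the hold applies whichever table is open.

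**Frequency.** The pilot reported Grade 2 pneumonitis in 3% of 34 patients: 0.03 × 34 = 1.02, so about one patient. At that rate, the most likely enrolment of 46 gives 0.03 × 46 = 1.4 patients, and the maximum of 65 gives 0.03 × 65 = 1.95.

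**The case against.** The strongest reply is that most of this is difference of emphasis. Both sections want other causes excluded, and the wording in Table 5.4 joins evaluation and steroids without saying that steroids precede the result. The core drug actions agree. Section 5.4.1 offers its plan as suggested, whereas the hold rule in Section 5.2.2 is mandatory. A careful site could apply both tables together.

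Much of that stands. It reduces the first difference to an unclear sequence, and it disposes of any claim of contradiction over steroid dose and prophylaxis, where Table 5.6 is merely silent. It does not reach the Grade 2 taper or the restart schedule. Softer wording does not settle precedence either, since Table 5.4 is itself headed as guidelines. The external guidance document is cited in Table 5.6 only for Grades 3 and 4, so that citation does not resolve the Grade 2 wording.

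A reader might go further and infer that an Arm A patient managed from Table 5.6 keeps taking vorinostat, and that exposure before the 24-week endpoint is therefore affected. The documents do not support this. Table 5.6 nowhere says that vorinostat continues, and continuing it would breach the hold rule in Section 5.2.2. A reader might also count the missing taper at Grades 3 and 4 as a conflict. With the cited guidance document not available here, that silence proves nothing.

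**Conclusion.** The point holds as an internal inconsistency: two clear differences (Grade 2 taper and restart schedule), one unclear sequence (steroid start), and three omissions in Table 5.6 that leave the rules of Section 5.2.2 intact.

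Its reach is small in numbers. One or two Grade 2 cases is a rough guide that assumes the pilot rate applies to both arms and to a biomarker-selected population. All pilot patients were on a vorinostat regimen, six of the 34 never received pembrolizumab, and a single event cannot fix a rate. The recommendation does not depend on that count, nor on any effect on the primary analysis. It rests on patients with the same event being managed in the same way, and on staff being able to tell which instruction binds them. No view is taken on which clinical instruction is right.

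**What to change.** Reconcile Sections 5.2.2 and 5.4.1 so that one instruction governs when steroids start relative to evaluation, whether the taper at Grade 2 is conditional, and whether the pembrolizumab interval may change on restart. The interval wording in Section 5.1 should be brought into line at the same time. Add a cross-reference from Section 5.4.1 to Table 5.4 and to the hold rule under the attribution and holding paragraphs of Section 5.2.2, so that a reader of Table 5.6 alone also finds the steroid dose, the prophylaxis and the partner-drug rule.

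The sponsor's medical lead should decide which text governs. Each table contains material the other lacks; the Grade 1 row, the mention of infliximab and the 12-week return window appear only with Table 5.6. Any merger should therefore account for both sets and not simply drop one. The cost is an amendment to protocol wording, with no added procedures, visits or patients.

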## 6 Study Procedures and Schedule of Events

The study-specific procedures and assessments are detailed in this section and outlined in the Study Calendar – Section 6.1.

Screening assessments must be performed within 28 days prior to the first dose of investigational product unless otherwise noted. Any results falling outside of the reference ranges may be repeated at the discretion of the investigator.

All on-study visit procedures are allowed **a window of  $\pm$  5 days** unless otherwise noted. Treatment or visit delays for public holidays or weather conditions or patient’s personal reasons that do not compromise safety do not constitute a protocol violation. Treatment delays may not exceed 3 weeks unless discussed with the study team for patients with documented benefit. Patients with proven systemic benefit, who have localized progression in the sanctuary site, may receive localized treatment to that site, including but not limited to radiation therapy, gamma knife or surgery.

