### **5.4 Discontinuation and Withdrawal**

Participants may discontinue study treatment at any time for any reason or be dropped from the study treatment at the discretion of the investigator should any untoward effect occur. In addition, a participant may be discontinued from study treatment by the investigator or the Sponsor if study treatment is inappropriate, the trial plan is violated, or for administrative and/or other safety reasons. Specific details regarding procedures to be performed at study treatment discontinuation are provided in Section 6.3.2.6 – Study Procedures Restaging or Off-Study Visit.

A participant must be discontinued from study treatment but continue to be monitored in the study for any of the following reasons:

- The participant or participant's legally acceptable representative requests to discontinue study treatment
- Confirmed radiographic disease progression outlined in Section 3.5.
- Any progression or recurrence of any malignancy, or any occurrence of another malignancy that requires active treatment
- Unacceptable adverse experiences, as described in Section 7.3.5.
- The participant has a medical condition or personal circumstance which, in the opinion of the investigator and/or sponsor, placed the participant at unnecessary risk from continued administration of study treatment.
- The participant has a confirmed positive serum pregnancy test
- Noncompliance with study treatment or procedure requirements
- Recurrent Grade 2 pneumonitis
- Discontinuation of treatment may be considered for participants who have attained a confirmed complete response (CR) and have been treated for at least 8 cycles (at least 24 weeks), receiving [for monotherapy: at least 2 doses of pembrolizumab; for combination treatment: 2 cycles of the combination including 2 doses of pembrolizumab and at least 80% of the planned doses of vorinostat beyond the date when the initial CR was declared. These participants may be eligible for second-course treatment described in Section 5.3.

- The participant is lost to follow-up
- Completion of 35 treatments (approximately 2 years) with pembrolizumab. (Patients may continue vorinostat and tamoxifen.)

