## 6.1 Study Calendar

Period/ Procedure	Pre- Screening	Screening 	Cycle 1			Cycle 2	Future Cycles 	Restaging or Off-Study Visit Survival Follow-up
Study Day/Visit Day*	-365 to -28	-28 (±3)	1 (±3)	10-12 (±3)	15 (±3)	1 (±3)	1 (±3)	9 weeks Post Start of Tx (±7)
Study Treatment/Drug Administration								
Pembrolizumab			200 mg q every 3 weeks; start on C1D1					
Vorinostat			400 mg once a day, 4 days on, 3 days off, weekly every cycle					
Tamoxifen			20 mg once a day continuously					
Administrative Procedures								
Prescreening ICF	X							
Informed consent		X						
Clinical Assessments								
Physical exam		X	X		X	X	X	
Vital signs		X	X		X	X	X	
Performance status		X	X		X	X	X	
Medical history		X						
Concomitant medications		X	X		X	X	X	
Toxicity Assessment 		X	X		X	X	X	X 
Drug Diaries 			X			X	X	
Documentation of Response		X					X	

 All screening procedures must be performed within 28 days unless otherwise indicated. Pre-study tests, History and Physical may be used for Day 1 tests if within 2 weeks

 Cycle delays up to 14 days for non-medical reason (e.g. holidays) are acceptable without notification of regulatory agencies

 Therapy delay for palliative radiation should be based on discussion with the study sponsor and the treating physician, every effort should be made not to hold therapy, patients, where vorinostat is being held for more than 4 weeks, may stay on study if there is felt to be a benefit

 Toxicity assessment must be performed until all treatment-related toxicities have been resolved or decreased to grade 1. Adverse events must be recorded up to 30 days after termination on study

 Drug diaries will be administered for vorinostat and tamoxifen (oral drugs) only on the first day of every cycle

Period/ Procedure	Pre- Screening	Screening 	Cycle 1			Cycle 2	Future Cycles 	Restaging or Off-Study Visit Survival Follow-up
Study Day/Visit Day*	-365 to -28	-28 (±3)	1 (±3)	10-12 (±3)	15 (±3)	1 (±3)	1 (±3)	9 weeks Post Start of Tx (±7)
Laboratory Assessments								
Hematology 		X	X		X	X	X	
Comprehensive Metabolic Panel 		X	X		X	X	X	
Thyroid Function 		X				X	X (odd cycles)	
Tumor Markers 		X	X			X	X	
Pregnancy test 		X					X	

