## **6.6 Prohibited Medications**

Subjects are prohibited from receiving the following therapies during the Screening and Treatment Phase (including retreatment for post-complete response relapse) of this trial:

- Anti-cancer systemic chemotherapy or biological therapy
- Immunotherapy not specified in this protocol
- Chemotherapy not specified in this protocol
- Investigational agents other than Pembrolizumab
- Radiation therapy

- Note: Radiation therapy to a symptomatic solitary lesion or the brain may be allowed after consultation with the study PI and Merck.
- Live vaccines within 30 days prior to the first dose of trial treatment and while participating in the trial. Examples of live vaccines include, but are not limited to, the following: measles, mumps, rubella, chicken pox, yellow fever, rabies, BCG, and typhoid (oral) vaccine. Seasonal influenza vaccines for injection are generally killed virus vaccines and are allowed; however, intranasal influenza vaccines (e.g., Flu-Mist®) are live attenuated vaccines and are not allowed.
- Glucocorticoids for any purpose other than to modulate symptoms from an event of clinical interest of suspected immunologic etiology. The use of physiologic doses of corticosteroids may be approved after consultation with the study PI and Merck.

Subjects who, in the assessment by the investigator, require the use of any of the aforementioned treatments for clinical management should be removed from the trial. Subjects may receive other medications that the investigator deems to be medically necessary.

The Exclusion Criteria describes other medications, which are prohibited in this trial.

There are no prohibited therapies during the Post-Treatment Follow-up Phase.

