### 8.3.2 Primary Analysis (or Analysis of Primary Endpoints)

#### Primary Endpoint 1 Analysis (Evaluation of Efficacy)

For each arm objective response rate (ORR) will be defined as the proportion of participants randomized to that arm whose status is SD or better (CR, PR) at 24 weeks' follow-up. Within each treatment arm, the observed ORR will be compared to the respective null (ineffective) rate using the decision rule provided by the Simon's two-stage design. In addition to calculating the ORR, we will calculate the corresponding one-sided 95% confidence interval by appropriately accounting for the Simon's two-stage design: given the observed response number ( $s$ ), testing of the null hypothesis of  $H_0: p \leq p_0$  will reject the null if the probability of observing as many or less than the observed number of responses ( $s$ ) is less than the significance level:  $\text{Prob}(S \leq s | p_0) < \alpha$ . Using this hypothesis inversely, we can construct a  $(1-\alpha)100\%$  one-sided confidence interval is given as a set

$$\{p: \text{Prob}(S \leq s | p_0 = p) < \alpha\}$$

where  $\text{Prob}(S \leq s \mid p_0 = p)$  indicates the joint distribution of stage to stop and observed response number ( $s$ ) as in Chang et al., 1989. Similarly, the observed rates will be compared between the treatment arms using the Z-test and appropriately accounting for the Simon's two-stage design.

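### The documents give two answers on whether a sanctuary-site progression treated locally before week 24 counts as a success, and their rules on keeping such a patient do not agree

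*Combined protocol and SAP*

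**What the plan says.** **Permission.** The opening text of Section 6 states: "Patients with proven systemic benefit, who have localized progression in the sanctuary site, may receive localized treatment to that site". On the kinds of treatment, it says that such patients "may receive localized treatment to that site, including but not limited to radiation therapy, gamma knife or surgery". Neither the sanctuary site nor proven systemic benefit is defined, and no approval is required. The sentence stands among rules on visit windows and treatment delays. It implies continued participation but does not say so.

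**Scoring.** Section 8.3.2 counts "participants randomized to that arm whose status is SD or better (CR, PR) at 24 weeks" of follow-up. It sets no condition on earlier progression and has no rule for a lesion treated locally.

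**Other response rules.** The Section 2.2 table closes the primary endpoint's time frame at progression or death, up to 24 weeks. Section 7.1.4 records best overall response only up to progression, and ends stable disease once the progression criteria are met.

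**Continuation.**
- Section 3.5 treats until progression.
- The first list in Section 5.4 stops study treatment, with monitoring continued, for "Any progression or recurrence of any malignancy, or any occurrence of another malignancy that requires active treatment".
- The second list in Section 5.4 takes a patient with confirmed radiographic progression off the trial, but a note allows an exception for a patient who is clinically stable or improving.
- Section 6.6 prohibits radiation, with one exception: "Radiation therapy to a symptomatic solitary lesion or the brain may be allowed after consultation with the study PI and Merck". Other patients who "require the use of any of the aforementioned treatments for clinical management should be removed from the trial".
- Section 3.1 lets clinically stable patients with imaging progression stay on study and be restaged.
- Footnote 3 of the Section 6.1 calendar foresees radiation during the study: "Therapy delay for palliative radiation should be based on discussion with the study sponsor and the treating physician".

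**The concern.** Suppose a patient shows benefit, progresses in a sanctuary site at the week 9 or week 18 scan, has that site irradiated or resected, and continues. Section 8.3.2 read alone asks only for status at 24 weeks. If the treated site is then quiet and the rest of the disease is stable, the patient can be entered as SD and so as a success. If the treated lesion was a target, removing it also lowers the sum of diameters. Under Sections 2.2 and 7.1.4 the same patient stopped being a success at the progression.

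The investigator knows the arm, judges whether benefit is proven, and decides on local treatment. The count that drives each arm's go/no-go decision could then depend on which passage is followed, and use of local treatment could differ between arms.

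**Working it through.** **1. The plan's own design figures reproduce.** Inputs from Section 8.1.1:
- Arm A: n1 = 13, stop if 2 or fewer; n = 35, reject if 10 or more; null 0.15, alternative 0.40.
- Arm B: n1 = 11, stop if 1 or fewer; n = 30, reject if 7 or more; null 0.10, alternative 0.35.

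With r1 the stage 1 stopping limit and r the final cut-off:

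P(reject | p) = Σ over x from r1+1 to n1 of Bin(x; n1, p) × P[Bin(n − n1, p) ≥ r − x]

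Arm A gives type I error 0.0249 and power 0.904. Arm B gives 0.0220 and 0.900. The plan states 0.025 and 0.9 for each arm, so there is no arithmetic error.

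**2. How one patient reads under each rule** (progression in the sanctuary site at week 18, treated locally, no further growth):

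| Rule | Result |
|---|---|
| 8.3.2, status at 24 weeks | SD or better possible: success |
| 2.2, time frame | closed at progression |
| 7.1.4, best overall response | nothing after progression counts |
| 7.1.4, duration of stable disease | ended at week 18 |
| 7.1.4, PFS | event at week 18 |

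The timing allows this. Calendar footnote 13 schedules scans at weeks 9 and 18 and then after cycle 9, which is 9 × 3 = week 27. No scan is scheduled at week 24, so local treatment can fall between the scan that shows progression and the one that informs 24-week status.

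**3. Whether the patient stays.** Take an asymptomatic site outside the brain.
- Section 6 permits radiation to it if it counts as a sanctuary site.
- Section 6.6 does not permit that radiation and removes the patient. It does not list surgery.
- Section 3.5 and the first list in Section 5.4 end study treatment.
- The second list in Section 5.4 ends participation on confirmed progression unless its exception is used.
- Section 3.1 and calendar footnote 3 point towards staying.

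For a symptomatic solitary lesion or the brain, Sections 6 and 6.6 overlap, except that Section 6.6 requires consultation and Section 6 does not.

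**4. Illustration of size.** The documents give no frequency. **Assumption:** treated progressions counted as successes add 2 or 3 percentage points to the null success rate. For scale, one patient is 1/35 = 2.9 points in Arm A and 1/30 = 3.3 points in Arm B. The formula in step 1, with the cut-offs unchanged, gives:

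| Points added | Arm A: pass stage 1 | Arm A: type I error | Arm B: pass stage 1 | Arm B: type I error |
|---|---|---|---|---|
| 0 | 0.308 | 0.025 | 0.303 | 0.022 |
| 2 | 0.385 | 0.053 | 0.387 | 0.052 |
| 3 | 0.423 | 0.073 | 0.429 | 0.074 |

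If treated progressions count as failures, the first row applies.

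**The case against.** The strongest reply is that Section 8.3.2 should be read together with Section 7.1.4. On that reading stable disease has ended at progression, a later fall in the sum of diameters earns nothing, and any new lesion is progression whatever the targets do. Section 1.3.1 also reports clinical benefit in the earlier studies as a duration of stable disease. This is a fair reading and probably the intended one. However, Section 8.3.2 is the operative definition and refers to none of these rules. Section 5.2.4 shows that the plan can state such a rule: it excludes Second Course events from the primary analysis. Local treatment has no equivalent.

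A reader might infer more than the documents support:
- **That any single-site progression may be treated and kept.** The permission is limited to a sanctuary site in patients with proven systemic benefit. The terms are loose, but they restrict it.
- **That the plan scores these patients as successes.** Only the Section 8.3.2 sentence, read alone, does so. The documents as a whole are inconsistent.
- **That every other passage contradicts the permission.** Calendar footnote 3 and Section 3.1 support staying on study, and Sections 5.4 and 6.6 carry exceptions.
- **That local treatment moves PFS.** Section 7.1.4 dates the event at progression, and later treatment of the lesion does not change that date.
- **That removed patients leave the analysis.** Section 8.3.1 keeps all randomized patients in the efficacy analysis.

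**Conclusion.** The concern holds as an inconsistency in the primary endpoint and in the rules for continuing after progression. A sanctuary-site progression treated locally before week 24 is a possible success under Section 8.3.2 and a failure under Sections 2.2 and 7.1.4. The permission in Section 6 does not fit Sections 3.5, 5.4 and 6.6.

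The size is unknown. An assumed 2 to 3 points at the null would roughly double to triple per-arm type I error, to 0.05–0.07. A reader might be tempted to assume 10 points, which gives 0.33 in Arm A and 0.35 in Arm B. That would raise the null success rate by two thirds in Arm A (0.15 to 0.25) and double it in Arm B (0.10 to 0.20). Nothing in the documents supports this for so restricted a group. The design's stated error rates are correct as calculated, and the point should be settled because each stage 1 decision can turn on one patient.

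**What to change.** **Section 8.3.2.** Define a success as CR, PR or SD at the 24-week assessment with no RECIST 1.1 progression at any site beforehand, in line with Section 7.1.4. State that a patient with earlier progression, including at a site then treated locally, is a non-responder in the randomized arm whether or not study treatment continues. The PFS definition needs no change.

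**Reconciliation.** Sections 3.1, 3.5, 5.4, 6, 6.1 (footnote 3) and 6.6 must be reconciled so that one statement, the same in both arms, governs local treatment and continuation after progression. Which clinical rule to adopt is for the sponsor and investigators; the scoring rule works under any of them.

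**Data.** Record local treatment on the CRF (site and date).

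**Cost.** A few sentences in Section 8.3.2, one reconciled passage and a CRF item. Observed rates may fall slightly. Enrolment, cut-offs and the stated error rates are unchanged.
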